4.1.12.5 Multiple imputation under MAR hypothesis

Using the monotone datasets generated as described in Section 4.1.12.1, the remaining missing HbA1c or FPG data will be imputed separately for each treatment regimen and weight (as applicable) using a REGRESSION method in conjunction with the MONOTONE statement of the SAS MI procedure and MAR assumption.

- Step 1: Prior to imputation, the MCMC method will be used in the MI procedure to impute just enough missing values under a “missing at random” (MAR) model to generate 200 imputed data sets with a monotone missing data pattern. The imputation model will include factors and covariates in the following order: indicators of randomisation strata and baseline HbA1c/FPG as well as HbA1c/FPG at all visits per protocol prior to Week t.
- Step 2: Missing data will be imputed sequentially at each assessment using a MAR imputation based on all non-missing data from that visit and data from all prior visits (after imputation). The indicators representing randomisation strata will be included in the same order as described in Step 1. Therefore, the model will include, in the following order, indicators representing randomisation strata of sex, age group, and background medication as well as, baseline HbA1c/FPG, treatment regimen, and all previous HbA1c/FPG values (all visits per protocol prior to Week t).
- Step 3: Imputed values from each of the 200 imputation datasets selected from Step 2 and the non-missing data will be analysed by ANCOVA applied at Week t, with terms for baseline HbA1c, randomisation strata, and treatment regimen as described in Section 4.1.9. In case of non-convergence, the imputation model will be simplified removing/collapsing the randomisation strata indicator variables in a stepwise manner as described in Section 4.1.
- Step 4: Results from each ANCOVA model will be combined as described in Section 4.1.12.4.

4.1.12.6 Tipping point analysis

A series of analyses will be performed with increasing values of δ (where δ represents HbA1c [%]) until the analysis conclusion of a statistically significant treatment effect no longer holds. The value of δ that overturns the primary results will represent a tipping point. An interpretation of clinical plausibility of the assumption underlying the tipping point will be provided. Values of δ will be examined until a p-value >0.05000 is obtained for the difference between groups in LS Means.

Using the monotone datasets generated as described in Section 4.1.12.1 and Step 1 of either MI-RD (as described in Section 4.1.12.2) or MI-WO (as described in Section 4.1.12.3) dependent on if there is sufficient data to perform the MI-RD model (as specified in Section 4.1.12) the remaining steps will be performed:

- Step 2: The MI procedure will be used with a MONOTONE statement to impute the remaining monotone missing data in the multiple imputed data sets generated in the first step. The imputed data for Week 26 will first be estimated under the MAR assumption ($\delta=0$). In subsequent models, a common set of δ values will then be added to the MNAR imputed values for Week 26 for the active treatment regimens (only), while imputed values for the placebo treatment group remain with no δ addition.

For the first imputation model ($\delta=0$), 200 imputation datasets will be generated using the 200 monotone datasets generated in Step 1. For the subsequent imputation models ($\delta > 0$), the same monotone datasets as those used for the first imputation model will be used.

- Step 3: For each value of delta, imputed values from each of the 200 imputation datasets selected from Step 2 and the non-missing data will be analysed by ANCOVA applied at Week t, with terms for baseline HbA1c, randomisation strata and treatment group as described in Section 4.1.9. In case of non-convergence, the imputation and ANCOVA model will be simplified by removing/collapsing the randomisation strata indicator variables in a stepwise manner as described in Section 4.1.
- Step 4: For each value of delta, results from each ANCOVA model will be combined as described in Section 4.1.12.4.

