4.4 Primary efficacy endpoint analysis

4.4.1 Primary analysis of the primary endpoint

The primary efficacy analysis will compare the mean reduction in HbA1c from baseline at Week 26 between overall drug treatment (low-dose and high-dose) and placebo. The ITT estimand (which will be estimated using data regardless of premature treatment discontinuation, regardless of rescue medication initiation and with multiple imputation) will be evaluated as the primary estimand.

Listings of HbA1c and FPG results used for the efficacy analysis will be presented with flags to identify data collected prior to rescue medication initiation or treatment discontinuation.

The primary efficacy analysis will be performed using an ANCOVA model, as described in Section 4.1.9. Separate models will be used for dapagliflozin and saxagliptin analyses, and each analysis will include the (common) placebo control. Each model will have terms for baseline HbA1c value, treatment group, and randomisation strata variables (age group, sex and background medication). Missing values for Week 26 will be imputed using multiple imputation method assuming the data are not missing at random. No weights will be used in the multiple imputation or ANCOVA for this analysis.

An overview of the analysis steps are as follows:

- i) Impute missing Week 26 HbA1c data using multiple imputation (as described in Section 4.1.12).
- ii) Analyse data by applying the ANCOVA model (described in Section 4.1.9) in each of the imputed data sets to calculate the LS means and corresponding SEs for the adjusted mean changes within each treatment group as well as for the differences in adjusted mean changes

between treatment groups. If any stratification variables in the imputation model are collapsed, then the ANCOVA model will be collapsed correspondingly.

- iii) Combine point estimates and SEs using Rubin's rules (as per Section 4.1.12.4) to produce valid global estimates with corresponding p-values and CIs.

Combined LS means and 95% confidence intervals for the mean change in HbA1c for each treatment group as well as the difference in the estimated mean change between the dapagliflozin/saxagliptin treatment group and placebo will be calculated. The p-value of the difference in Week 26 estimates between dapagliflozin/saxagliptin and placebo will be presented.

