4.4.2.4 Tipping point analysis

To assess the robustness of the primary efficacy analysis for the primary endpoint of the change in HbA1c from baseline to Week 26, an additional sensitivity analysis using a tipping point will be performed at Week 26 as described in Section 4.1.12.6 for the same ANCOVA model used for the primary analysis (Section 4.4.1).

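### The tipping-point analysis names two imputation bases, MAR at delta = 0 and MNAR for positive deltas, and its starting point does not reproduce the MNAR primary analysis it is meant to test

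*SAP*

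**What the plan says.** SAP 4.1.12.6 describes a series of analyses with increasing delta until significance is lost. The delta "that overturns the primary results will represent a tipping point", and its clinical plausibility is to be interpreted.

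Step 2 gives the imputation rule. At delta = 0, "The imputed data for Week 26 will first be estimated under the MAR assumption". In later models a common set of deltas "will then be added to the MNAR imputed values for Week 26 for the active treatment regimens", while imputed placebo values receive no shift. What is held constant is stated only for the earlier stage: "the same monotone datasets as those used for the first imputation model will be used". The section also refers to MI-RD or MI-WO, "dependent on if there is sufficient data to perform the MI-RD model".

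For the primary analysis, SAP 4.4.1 says: "Missing values for Week 26 will be imputed using multiple imputation method assuming the data are not missing at random". SAP 4.1.12 prefers MI-RD and falls back to MI-WO if any required imputation model has fewer than five retrieved drop-outs. SAP 4.4.2.4 runs the tipping point "for the same ANCOVA model used for the primary analysis", which fixes the analysis model but not the imputation. Table 23 lists the tipping-point analysis as following the same approach as the primary one.

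**The concern.** A tipping point is read as a distance: how much worse than the base assumption the unobserved active-arm values must be before the conclusion changes. The reader has to know that base. The natural one is the primary imputation, because that is the result being stressed; delta = 0 should then return the primary estimate.

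Step 2 names MAR for the start and MNAR for what follows, and does not say what the MNAR imputed values are. They could be MI-RD or MI-WO draws, or MAR draws that count as MNAR once shifted. Two programmers could both comply and report different tipping points from the same data. The SAP requires a plausibility judgement on that number, and this is its only delta-adjusted test of the primary endpoint's missing-data assumption.

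**Working it through.** **Inputs.** Effect E = 0.75, SD 1.7, two-sided alpha 0.05 and power about 80% (SAP 1.3); 81 per arm (SAP 1.2). The fraction m of active-arm Week 26 values that is imputed is my assumption, since the current text gives none; I use 5%, 10% and 20%. Effects are written as reductions versus placebo, so a positive delta shrinks them.

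**The plan's own figure.** SE = 1.7 × √(2/81) = 0.267. Power = Φ(0.75/0.267 − 1.96) = 0.802, which reproduces the stated 80%. The smallest significant difference is c = 1.96 × 0.267 = 0.524.

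**What the monotone datasets fix.** SAP 4.1.12.1 creates them by MCMC, filling just enough gaps to leave a monotone pattern. The remaining Week 26 values are imputed afterwards. Reusing these datasets therefore does not fix the final imputation model.

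**Tipping delta on each base, with wash-out as the MNAR method.** Under MAR I assume that imputed active values carry the full effect E. Under wash-out they carry none.

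- MAR base: E − mδ = c, so δ = (E − c)/m.
- Wash-out base: E(1 − m) − mδ = c, so δ = (E(1 − m) − c)/m.
- Difference: (E − c)/m − (E(1 − m) − c)/m = E = 0.75 for every m.

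| Assumed m | MAR base | Wash-out base | Gap |
|---|---|---|---|
| 5% | 4.53 | 3.78 | 0.75 |
| 10% | 2.26 | 1.51 | 0.75 |
| 20% | 1.13 | 0.38 | 0.75 |

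**The literal series.** At m = 10% the estimate is 0.750 at delta = 0 under MAR. At delta = 0.1 on wash-out it is 0.75 × 0.90 − 0.10 × 0.1 = 0.665. The step moves it by 0.085, of which 0.010 is the shift and 0.075 the change of model. At m = 20% the next value is 0.75 × 0.80 − 0.20 × 0.1 = 0.580, a move of 0.170 where the shift alone accounts for 0.020.

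**Check with full machinery.** The formulas hold the SE at 0.267. A small simulation used multiple imputation, ANCOVA and Rubin's rules, with baseline as covariate and missing values in the active arm only. At 10% missing it gave MAR versus wash-out tipping points of 2.1 vs 1.2 and 1.3 vs 0.6 (effect set at 0.75), and 3.8 vs 2.6 and 4.0 vs 3.0 (effect set at 1.0). The gaps of 0.7 to 1.2 are close to the effect in each case.

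**MI-RD.** Its base comes from the Week 26 values of subjects who stopped treatment but stayed in the study. The documents give no such values, so no gap can be computed.

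**The case against.** A reader might infer that the base moves at every step and that the reported tipping point has no fixed meaning. The text does not support that. Read literally, there is one switch, and all positive deltas share one base. If the MNAR imputed values are MI-RD or MI-WO draws, a positive tipping point is already a departure from the primary imputation. On that reading the fix changes only the delta = 0 row.

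There is also a coherent alternative. The section equates MAR with delta = 0 and then shifts the active arms, which fits ordinary delta adjustment; nothing then jumps. Table 23 and the reference to MI-RD or MI-WO point instead to the primary method as the base. The 0.75 gap is thus a difference between two readings, not an error within either. It needs wash-out, although MI-RD is preferred, and it needs the MAR draws to carry the full effect. MAR imputation in SAP 4.1.12.5 conditions on earlier visits, while wash-out for the active arms uses strata and baseline only, so the real gap may be smaller or larger.

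All of this stands as a limit on the claim. It does not remove the point. SAP 4.1.12 reserves the term MNAR for MI-RD and MI-WO, which favours the literal reading, while the MAR start favours the other. Table 23 does not settle it, because an analysis that copies the primary one cannot begin under MAR. On both readings delta = 0 differs from the primary imputation.

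**Conclusion.** The point holds as an inconsistency in how the base is specified. The delta = 0 rule does not fit the section's own definition of the tipping point, and the wording admits two series. Under wash-out, with the planned 0.75% effect carried by the MAR draws, these differ by 0.75 HbA1c points whatever the missing fraction. That matters most when more data are missing: at an assumed 20%, the same trial could be described as robust to a shift of 1.13 points or of 0.38. For MI-RD the size is unknown.

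It should not be read as a flaw in the primary result. The primary test, alpha and sample size do not depend on this sensitivity analysis, and SAP 4.4.1 already presents the primary endpoint under both MI-RD and wash-out. Nor does it show that a reported tipping point would be wrong by 0.75; it shows that the reader could not tell which base it was measured from.

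**What to change.** In SAP 4.1.12.6 Step 2, replace the MAR start with the imputation method used for the primary analysis (MI-RD or MI-WO, as selected under 4.1.12), applied at every delta including 0. State that delta = 0 must reproduce the primary estimate, which also gives a programming check. Add delta only to imputed active-arm Week 26 values, and report the tipping point as a shift from that named base. If a MAR-anchored series is wanted, run it separately with MAR at every delta and label it so.

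The cost is about one sentence in the SAP and the matching program specification. No further data are needed.

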4.2 Study population

Study population data for the treatment period will be presented. A table presenting the number and percentage of subjects in the Randomised Subjects Data Set, Up-titration Randomised Subjects Data Set, Evaluable Subjects Data Set, Treated Subjects Data Set, Randomised Withdrawal Subjects Data Set and Pharmacokinetic Analysis Data Set will be provided. Subjects excluded from each analysis set and reason(s) for exclusion will be listed.

For the Randomised Withdrawal Subjects Data Set, subjects who passed Week 32/Week 40 prior to protocol amendment 4 being approved in their country were not eligible to qualify for this potential randomisation and will be presented under the reason for exclusion “Other” in the summary table.

4.2.1 Subject disposition

The subject disposition for the screening period, ST+LT period, randomised withdrawal period and post-study visit Week 104 will be summarised:

- Disposition for the screening period will be based on the Enrolled Subjects Data Set (who signed informed consent), and will include the number of subjects enrolled, passed the screening period, discontinued from the screening period and a summary of the corresponding reasons for discontinuation. The number of rescreens and total number of times rescreened will also be presented for subjects who were rescreened.

- Disposition for the combined ST+LT treatment period will be based on the Randomised Subjects Data Set and will be presented by randomised treatment group and overall using overall treatment regimen and placebo. This summary will include subjects that entered the ST treatment period, completed the ST treatment period, discontinued from the study during the ST treatment period and reasons for study discontinuation, discontinued treatment during the ST treatment period and reasons for treatment discontinuation, subjects up-titration status, subjects that entered the LT treatment period, completed the LT treatment period, discontinued from the study during the LT treatment period and reasons for study discontinuation, discontinued treatment during the LT treatment period and reasons for treatment discontinuation, and subjects who completed the 56-week visit.
In addition, for Week 104 follow-up CSR the summary will also include the number of subjects who continued into the post-term extension, completed the Week 104 visit, discontinued during the post-term extension.
- Disposition for the randomised withdrawal period will be based on the Randomised Withdrawal Subjects Data Set. This will be presented by randomised treatment group for the 1st and 3rd randomisations and overall. This summary will include the number of subjects who went through the 3rd randomisation, were randomised to withdrawal from Metformin, completed the randomised withdrawal period, discontinued from the randomised withdrawal period and a summary of the corresponding reasons for discontinuation, completed IP during the randomised withdrawal period, discontinued IP during the randomised withdrawal period and a summary of the corresponding reasons for IP discontinuation, and subjects who completed the 56-week visit.
- The number of subjects completing the study and who discontinued the study related to the global/country situation will be tabulated by discontinuation reason separately for the ST period, ST+LT period, and Week 104 follow-up period.

In addition, subjects from Randomised Subjects Data Set will be summarised by country and study site.

Subject disposition will also be listed by subject.

4.2.2 Global/country situation impact

An overall summary of the number and percentage of subjects in the study during the global/country situation will be provided using the Randomised Subjects Data Set, including:

- Subjects randomised prior to the start of the global/country situation (prior to 11 March 2020),
- Subjects who are no longer in the study at the start of the global/country situation (discontinued study or completed Week 104 visit),
- Subjects ongoing in the study at the start of the global/country situation,
 - Subjects in the ST+LT period (up to Week 56),
 - Subjects in the Week 104 follow-up period,

- Subjects randomised after the start of the global/country situation.

Furthermore, the number and percentage of subjects impacted by the global/country situation will be presented overall and by impact category (visit impacted, study drug impacted, drug accountability impacted, concomitant medication not started, withdrawal from study due to global/country situation).

Important protocol deviations that are related to the global/country situation will be summarised within the important protocol deviation table by deviation category. These will be identified using protocol deviations starting with the word “COVID”.

In addition, to capture supplementary information on the global/country situation impact, details on visits impacted, concomitant medications not started, dispensation or returning of study medication kits, and exposure start dates that were impacted will be collected. Details on the global/country situation data will be listed by-subject using the Enrolled Subjects Data Set. This will be presented for the Week 56 CSR using all data up to Week 56 database lock and also for the Week 104 CSR addendum using all data up to Week 104 database lock.

4.2.3 Demographic and other baseline characteristics

Frequency distributions and summary statistics for demographics and baseline characteristics (age, sex, race, ethnicity, baseline body weight, normalised baseline body weight, baseline height, normalised baseline height, baseline BMI, normalised baseline BMI, and region), including diabetes-related characteristics (duration of type 2 diabetes, baseline HbA1c, baseline FPG, background antidiabetic medication, total daily dose of metformin and insulin, and baseline renal function [eGFR]) will be summarised by treatment group based on first randomisation and overall using the Randomised Subjects Data Set, the Up-titration Randomised Subjects Data Set, the Randomised Withdrawal Subjects Data Set and, if deemed necessary, the Evaluable Subjects Data Set. No statistical test will be carried out for comparison of demographics or baseline characteristics among the treatment groups.

Randomisation stratification factors (including age group, sex, and background antidiabetic medication) will be summarised by treatment group based on first randomisation and overall using the Randomised Subjects Data Set. A listing of differences between the stratification factors recorded on the IWRS and collected on the CRF will be presented. For age, only subjects with a complete date of birth collected will be compared.

4.2.4 Specific and general medical history

The number and percentage of subjects with general medical history findings and current medical conditions will be summarised by SOC and PT (sorted by decreasing frequency by SOC and PT based on the total group) by treatment group and overall using the Randomised Subjects Data Set. All medical history details will be listed.

4.2.5 Prior and concomitant medications

The number and percentage of subjects taking concomitant medications will be summarised for the ST and ST+LT periods by WHO DD ATC classification, generic term and treatment group

based on the Treated Subjects Data Set. Concomitant medications will be listed for the combined ST+LT period and in addition during the study. Prior medications will not be included in the summaries but will be included and identified in the medications listing.

Concomitant anti-diabetes medications will be recorded over the course of the study and will be included in concomitant medication summaries. These will also be summarised separately by insulin anti-diabetes concomitant medications and non-insulin anti-diabetes concomitant medications (as described in Section 3.5.3). A separate table will be presented for insulin anti-diabetes concomitant medications used as rescue medication.

In addition, a summary of disallowed medications (as defined in the protocol) will be provided for each period. Disallowed medications used concomitantly during the study will be flagged in the listings.

A summary of all concomitant medications started between Week 56 and Week 104 (regardless of protocol defined disallowed medications) will be provided.

Separate listings for the ST+LT period will be provided for background metformin and background insulin and a further listing will be provided for insulin as rescue medication.

4.3 Extent of exposure to study treatment

4.3.1 Extent of exposure to IP treatment

Extent of exposure to IP will be summarised (regardless of rescue medication initiation) using the Treated Subjects Data Set for the ST and ST+LT treatment periods, and the Randomised Withdrawal Subjects Data Set for the randomised withdrawal period. These summaries will be repeated for exposure prior to rescue medication initiation.

Extent of exposure is defined as last dose date - first dose date + 1, with the last dose date being the last dose of the concerned period. Extent of exposure (days) will be summarised by treatment group as a continuous variable as well as for pre-specified day ranges (ST period: 1-7, 8-14, 15-28, 29-42, 43-56, 57-70, 71-84, 85-98, 99-140, 141-182, > 182 days; ST+LT period: 1-90, 91-180, 181-270, 271-365, and > 365 days; randomised withdrawal period: 1-7, 8-14, 15-28, 29-42, 43-56, 57-70, 71-112, 113-154, > 154). In addition, the exposure in terms of total patient-years will be summarised by treatment group using the sum of the exposure to IP of all subjects (in years) in a treatment group.

Individual subject dosing and exposure to IP by study period will be listed.

A listing of subjects by batch number of study medication will also be generated.

